4.0 SUBJECT ELIGIBILITY AND WITHDRAWAL CRITERIA

Subjects who do not meet eligibility criteria will be classified as screen failures and the reason(s) will be recorded in the case report form (CRF)/electronic CRF (eCRF).

4.1 INCLUSION CRITERIA

4.1.1 Pre-exercise Inclusion Criteria

Subjects are eligible for the study if all of the following criteria are met:

1. Subject must provide informed consent before any study-specific evaluation is performed.
2. Subject is male and female aged 18 to 35 years, inclusive.
3. Subject has a body mass index (BMI) of 18 to 32 kg/m², inclusive

■ [REDACTED]

■ [REDACTED]

6. Subject hematology, serum chemistry, urinalysis, vital sign measurements (systolic blood pressure, diastolic blood pressure, pulse rate, respiratory rate, and oral body temperature) and 12-lead ECG results show no clinically relevant abnormalities, as judged by the investigator at the Screening Visit.
7. All female subjects must have a negative serum pregnancy test result at Screening and negative urine pregnancy test on Day -1 prior to admission to the clinic. Female subjects of childbearing potential must use one of the following acceptable birth control methods as specified before enrollment and throughout the study:
 - a. Surgical sterilization (bilateral tubal ligation, hysterectomy, bilateral oophorectomy) at least 6 months before the first dose of study gel;
 - b. Intrauterine device in place for at least 3 months before the first dose of study gel and throughout the study;
 - c. Barrier method (condom or diaphragm) with spermicide for at least 14 days before the first dose of study gel and throughout the study;
 - d. Surgical sterilization of the male partner (vasectomy at least 6 months before the first dose of study gel);
 - e. Hormonal contraceptives for at least 3 months with a barrier method 14 days before the first dose of study gel and throughout the study;
 - f. Abstinence.
8. Subject is able and willing to comply with the protocol and study procedures.
9. Subject has negative test results for drugs and alcohol at screening and is able and willing to abstain from marijuana and alcohol use for 4 days before Day 1 and throughout the study. Note that a positive screening result for marijuana is acceptable provided the subject will abstain for the study as described above.

10. Subject does not use nicotine or has quit using nicotine for at least 6 months before the first dose of study gel and will not use nicotine throughout the study.

[REDACTED]

4.2 EXCLUSION CRITERIA

Subjects are excluded from the study if any of the following criteria are met:

- 1. [REDACTED]
- 2. [REDACTED]

3. Subject has received oral or topical analgesic medications within 14 days before the Screening Visit.
4. Subject has used a systemic corticosteroid within 30 days before the Screening Visit.
5. Subject has a medical history that includes a contraindication to the use of menthol or NSAIDs (e.g., gastrointestinal ulcer, gastrointestinal bleeding).
6. Subject is taking medications or other substances contraindicated because of the nature of the study gel or the potential for drug interactions. This includes subjects with allergies to prescription or OTC products containing menthol or NSAIDs.

[REDACTED]

[REDACTED]

[REDACTED]

[REDACTED]

14. Subject is pregnant or nursing.
15. Subject has participated in an investigational drug study within 30 days before Screening.
16. Subject is a member or a family member of the professional or ancillary personnel involved in the study.
17. Subject has participated in other clinical trials for K-285.
18. Subject has abnormal findings or assessments that are clinically noteworthy.
19. Subject who, in the opinion of the investigator, should not participate in the study.

4.3 DISCONTINUATION AND WITHDRAWAL CRITERIA

Subjects may voluntarily withdraw from the study at any time and for any reason without prejudice to their future medical care by the investigator or at the study site. The investigator may discontinue treatment of a subject or withdraw a subject from the study under specific circumstances, described below. The primary reason(s) for discontinuation or withdrawal (by the subject or the investigator) will be documented and recorded in the case report form CRF/eCRF.

The subject will be discontinued from study gel if any of the following occur:

1. There is a deterioration in the subject's signs/symptoms and/or the subject develops a disease or condition that in the opinion of the investigator, would compromise the subject's safety by continuing in the study.
2. In the investigator's judgment, it is in the subject's best interests.
3. Violation of the protocol inclusion and exclusion criteria.
4. The subject begins to take any medication(s) that is excluded by the protocol.
5. It is determined that there is discoloration, exfoliation or erosion, edema, discharge, blistering, exudate, ≥ 2 point on dermal responses score (Section 5.2.6), and/or any other dermal change that in the opinion of the investigator, would compromise the subject's safety by continuing in the study at the application site. The process for discontinuation due to an application site reaction is described in Section 4.3.1 below.
6. Occurrence of serious adverse event(s).
7. Pregnancy.

The subject will be withdrawn from the study if any of the following occur:

1. The subject withdraws consent.

2. The subject is lost to follow-up.
3. Any of the conditions are met in [Section 6.5](#), Termination of the Study.
4. The subject is unable or unwilling to cooperate with study staff.
5. Death.

Subjects who discontinue or withdraw from the trial due to the above criteria or any other reason, will be encouraged to complete the final evaluations as detailed in [Table 2](#). If a subject declines to complete early termination procedures, this decision will be recorded in the case report form CRF/eCRF.

If a subject discontinues or withdraws from the study due to an AE, the subject will be asked to return to the clinic for, at a minimum, the evaluations scheduled for the EOS/ET Visit (Day 8/Day 22). If the AE has still not resolved, additional follow-up will be performed, as appropriate, and documented in the subject's medical records. As a minimum requirement, AEs must be followed for 30 days after the subject's last dose of study gel or until resolution or until unresolved AEs are judged by the investigator (or designee) to have stabilized.

If subjects are lost to follow-up, attempts to contact them must be made and documented in the medical records. Subjects who fail to return for a study visit will be contacted directly by the study staff. A minimum of 2 documented phone calls will be made. If the study staff receives no response, they will send a certified letter requesting that the subject contact the study site regarding his or her status in the study.

Discontinued or withdrawn subjects will not be replaced.

4.3.1 Discontinuation due to an Application Site Reaction

1. During a clinical site visit, the application site reaction will be assessed by study staff. If there are any significant findings, they will be noted in each subject's source documents.
 - If the application site reaction is judged to meet the discontinuation criteria ([Section 4.3](#)), the subject will be discontinued from the study.
2. During the out-patient period at home, application site reactions will be assessed by the subject. If any application site reaction is noticed, the subject will contact the site before dosing.
 - The subject will not apply study gel until receiving confirmation from the site to proceed.
 - If the subject contacts the site and then the application site reaction is judged to meet the discontinuation criteria ([Section 4.3](#)), the subject will be discontinued from the study. At that time, the subject will be asked to gather safety reference information as follows:
 - Record the score of dermal response ([Section 5.2.6](#)) in the e-diary. Reference images of application site reactions are shown in [Appendix 15.4](#).

5.0 PROCEDURES FOR EFFICACY AND SAFETY EVALUATIONS

5.1 EFFICACY EVALUATIONS

5.1.1 Pain Intensity

Prior to exercise to induce DOMS, pain will be assessed for both legs at rest and while standing using a 0-100 point paper VAS to exclude subjects with other pain.

Following exercise to induce DOMS, pain at rest and while standing will be assessed for both legs using a 0-100 point eVAS and a categorical pain scale to determine qualification for randomization and to identify the study leg (baseline assessment). All pain assessments will be recorded in the e-diary.

After randomization, pain at rest and while standing will be assessed for the study leg and the non-study leg using a 0-100 point eVAS at all post-study gel application time points in Period 1 (Table 2). When study gel application and pain assessment occur at the same time point, pain assessments will be performed before study gel application.

The subject will rest quietly for at least 5 minutes before assessing pain at rest for the study leg and non-study leg (the study leg will be assessed first). The subject will sit for at least 5 minutes, then stand up and rate the worst pain caused by standing (the act of moving from a sitting to standing position) for the study leg and non-study leg (the study leg will be assessed first).

5.1.1.1 Visual Analog Scale

The pain VAS, a unidimensional measure of pain intensity, is a continuous scale from 0 to 100 comprised of a horizontal line anchored by 2 descriptors, one for each symptom extreme: “no pain” (score of 0) and “worst possible pain” (score of 100). A paper version of the pain VAS will be used for pre-exercise pain assessments (Appendix 1).

The pain eVAS is electronically displayed and is completed by the subject for baseline and each post-randomization pain intensity assessment by touching the point on the eVAS that represents their pain intensity. (A capture program will linearly convert the pixel touched to an integer between 0 and 100). The integers of the eVAS will be referred to as points. The assessment date and time for the study leg and for the non-study leg is recorded in the e-diary (Appendix 1).

5.1.1.2 Categorical Pain Scale

A 4-point categorical pain scale (none, mild, moderate, severe) at rest will be used to assess pain intensity following the exercise session. A categorical pain scale is provided in Appendix 2.

5.1.2 Use of Rescue Medication

Use of any rescue medication for DOMS is strongly discouraged until 168 hours after the first study gel application, at which time OTC acetaminophen (one 500 mg acetaminophen tablet twice daily, not more than every 6 hours) as rescue medication is permitted if required.

Subjects experiencing severe pain, or inability to move or walk due to pain, may be permitted to use rescue medication (one 500 mg OTC acetaminophen tablet twice daily, not more than every 6 hours) prior to 168 hours after the first study gel application. If subjects take rescue medication within the first 168 hours after the first study gel application, it will be recorded in the e-diary as rescue medication, and entered into the eCRF as a concomitant medication, and will be programmatically categorized as a concomitant medication. Subjects will record their pain intensity in the e-diary before taking the rescue medication. The number of tablets taken and the date and time will be recorded in the e-diary.

5.1.3 Time to Onset of First Perceptible and Meaningful Pain Relief

Pain assessments of time to first perceptible pain relief and time to meaningful pain relief for both legs at rest and while standing will be recorded by subjects using their e-diary until achieved in Period 1. At the time of first perceptible pain relief and at the time of meaningful pain relief, subjects will use their e-diary to record the time the events are experienced. Since these assessments will be captured in the e-diary, the electronic database will be the direct point of data capture and will serve as source for this variable.

5.1.3.1 Onset of Perceptible Pain Relief

Onset of perceptible pain relief will be assessed for the study leg and non-study leg at rest and while standing by responding “no” or “yes” to a question such as the following example:

Please confirm that you would like to report that you have experienced perceptible pain relief at **REST/while STANDING** in your **STUDY/NON-STUDY** leg. Please note that “perceptible pain relief” means any pain relief at all. If you feel the pain is getting even a little bit better, then please answer “YES.”

5.1.3.2 Onset of Meaningful Pain Relief

Onset of meaningful pain relief is assessed for the study leg and non-study leg at rest and while standing only after onset of perceptible pain relief has been achieved. The subject responds “no” or “yes” to a question such as the following example:

Please confirm that you would like to report that you have experienced meaningful pain relief at **REST/while STANDING** in your **STUDY/NON-STUDY** leg. Please note that “meaningful pain relief” is “When the relief from pain is meaningful or significant to you.” This does not necessarily mean that you feel completely better, although you might. Remember to tell the Diary when you first experience meaningful pain relief.

5.2 SAFETY EVALUATIONS

5.2.1 Adverse Events

Adverse events will be recorded according to the schedule in [Table 2](#). All AEs, whether ascribed to study procedures or not, will be documented on the eCRF and will include the date and time of onset, a description of the AE, severity, duration, actions taken, outcome, and the relationship between the study gel and the event. Any subject who discontinues/withdraws from the study due to an AE will be followed up until the outcome is determined and written reports are provided by the investigator. Adverse event

definitions, and reporting and follow-up requirements are described in Section 9.1, 9.2, and 9.3, respectively.

5.2.2 Clinical Laboratory Tests

Clinical laboratory tests will be performed by a central laboratory. Blood samples will be collected according to the schedule in Table 2 and processed as detailed in the Laboratory Manual.

Urinalysis will be performed by a central laboratory according to the schedule in Table 2. Urine samples will be collected and processed as detailed in the Laboratory Manual. If microscopy is required, a urine sample will be sent to the local laboratory.

The parameters being measured are shown in Table 3.

Table 3. Clinical Laboratory Test Parameters

| Hematology | Clinical Chemistry | Urinalysis |
|------------------------------------|---|--|
| Basophils | Alanine aminotransferase | Bilirubin |
| Eosinophils | Albumin | Blood |
| Hematocrit | Alkaline phosphatase | Glucose |
| (Packed cell volume) | Aspartate aminotransferase | Ketones |
| Hemoglobin | Bicarbonate | Leukocytes |
| Lymphocytes | Bilirubin (total) | Nitrites |
| Mean cell hemoglobin | Bilirubin (direct; only if total is elevated) | pH |
| Mean cell hemoglobin concentration | Calcium | Protein |
| Mean cell volume | Chloride | Specific gravity |
| Monocytes | Creatine kinase ¹ | Urobilinogen |
| Neutrophils | Creatinine | At the discretion of the investigator based on urinalysis results Microbiology Urine Microscopy |
| Platelet count | Follicle-stimulating hormone (post-menopausal female patients only) | |
| Red blood cell count | Gamma glutamyl transferase | |
| White blood cell count | Triglycerides | |
| | Glucose (fasting) | |
| | Human chorionic gonadotropin (all female patients) | |
| | Lactate dehydrogenase | |
| | Magnesium | |
| | Potassium | |
| | Phosphate (inorganic) | |
| | Protein (total) | |
| | Sodium | |
| | Blood urea nitrogen (BUN) | |
| | Uric acid | |

¹ Elevated levels of creatine kinase are expected as a result of the exercise performed on Day -1 and will be handled as described in Section 5.2.2.1.

5.2.2.1 Elevated Levels of Serum Creatine Kinase

Elevations of serum creatine kinase (CK) are expected to occur as a consequence of the exercise performed on Day -1 and will not be reported as AEs. Additional safety steps will be taken to monitor the subjects for signs of rhabdomyolysis. If a subject has a serum CK above 10,000 U/L (and associated elevations of lactate dehydrogenase [LDH], aspartate aminotransferase [AST], or alanine aminotransferase [ALT]), but no significant signs or symptoms of rhabdomyolysis other than muscle pain and swelling at the exercised muscles,

the following actions will be taken with the subject until the EOS Visit (Day 8 for subjects dosing during Period 1 and Day 22 for subjects dosing during Period 2):

- Subjects will be instructed to monitor the urine for changes in color carefully.
- Subjects will be instructed to report any urine discoloration, such as dark yellow, brown, cola or tea colored urine, to study personnel.
- Subjects will be instructed to maintain adequate hydration at home (approximately 15.5 cups [3.7 liters] of fluids for males and 11.5 cups [2.7 liters] of fluids a day for females)

In addition, the following actions may be taken with the subject at the discretion of the investigator:

- Subjects will be asked to stay overnight at the study site where vigorous hydration will be administered and monitoring for any clinical signs or symptoms of rhabdomyolysis will be undertaken. The subject will be released when, per the investigator's discretion, it is appropriate to do so. Prior to release, the sponsor's Medical Monitor will be notified.
- Subjects will have a serum CK clinical laboratory repeated as clinically indicated.
- Subjects will have a urinalysis repeated as clinically indicated.

If there is an elevation in CK and rhabdomyolysis is suspected, the work-up should also include evaluation of CK Panels (total CK, CK-myocardial band [CK-MB], CK in skeletal muscle [CK-MM] and CK in brain [CK-BB]), troponin, creatinine, myoglobin (serum and urine), transaminases, total bilirubin levels, and urinalysis including urine sediment. A physical examination should be performed to document findings such as muscle tenderness, weakness, or rash. An ECG should also be performed. Abnormalities should be followed until they have returned to baseline, or until the investigator considers them clinically stable.

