| Clinical laboratory tests (hematology, serum chemistry, and urinalysis) | X | | | | | | | | | X | |
| eVAS pain intensity assessments ^c (e-diary) | | | X | X | X | X | | | | (X) ^l | |
| Perceptible and Meaningful pain relief assessments ^c (e-diary) | | | | | X | | | | | (X) ^l | |
| Photographic and residue evaluation ^f | | | | X | | | | | | | |

| ASSESSMENTS PERFORMED | Screening Visit | Exercise Visit | Period 1 | | | Period 2 | | | | EOS Visit/ET ^k | Follow-up call |
|--|-----------------|----------------|------------|-------------|-------------|---------------|-------------|----------------|-------------|---------------------------|----------------------|
| | | | In patient | Out patient | Out patient | Safety Visit | Out patient | Safety Visit | Out patient | | |
| Day | -30 to -2 | -1 | 1 | 2 | 3-8 | 8 (±1 day) | 9-14 | 15 (±1 day) | 16-22 | 8 or 22 (+1 day) | 15 or 29 (±1 day) |
| Photographic evaluation of application site reactions ^g | | | (X) | (X) | (X) | (X) | (X) | (X) | (X) | (X) | |
| Dispense study gel | | | | X | | X | | X | | | |
| Apply study gel ^h | | | X | X | X | X | X | X | X | (X) | |
| Record adverse events | X | X | X | X | X | X | X | X | X | X | X |
| Record concomitant medications ⁱ | X | X | X | X | X | X | X | X | X | X | X |
| Record rescue medication use ^j (e-diary) | | | X | X | X | X | X | X | X | X | |
| Collect study gel | | | | | | | | | | X | |
| Collect subject e-diary | | | | | | | | | | X | |

██████████; DOMS, delayed onset muscle soreness; e-diary, electronic diary device; EOS, end of study; ET, early termination; ██████████ & ██████████; VAS, visual analog scale; (X), performed as indicated in the footnote.

- a Subjects will enter the clinic on Day 1 and will be discharged on Day 2 after study assessments at ██████████ study gel application are completed.
- b Study staff will contact subjects by telephone for assessment of AEs, skin condition and concomitant medications, and use of rescue medication. All subjects will be contacted on Day 5 (±1 day). Subjects participating in Period 1 will be contacted on Day 15 (±1 day). Subjects participating in Period 2 will be contacted on Day 11 (±1 day), Day 18 (±1 day), and Day 29 (±1 day).

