6.3 STUDY VISITS

Note: Timing of procedures and assessments are provided as examples. Actual timing may vary for each subject. Time points and time windows for study gel application and pain assessments are described in [Table 2](#).

- Day -30 to Day -2:
 - Screening Visit: The Screening Visit at the clinic to determine subject eligibility can take place anytime within this time period. Assessments include the following:
 - Informed consent
 - Demographics
 - Medical/medication history
 - Pre-exercise inclusion criteria, exclusion criteria
 - Height and weight
 - Vital signs
 - ECG
 - Physical examination
 - Skin examination / assessment at study gel site of both legs
 - Pregnancy test (serum) (females only)
 - Urine drug screen and alcohol test
 - Clinical laboratory tests (hematology, serum chemistry, and urinalysis)
 - Record AEs
 - Record concomitant medications
- Day -1:
 - Exercise Visit: On Day -1 procedures and assessments are as follows:
 - Update Medical/medication history
 - Pre-exercise inclusion and exclusion criteria
 - Pain assessment (pre-exercise to exclude subjects with other pain using a paper VAS)
 - DOMS induction exercise
 - Vital signs
 - ECG
 - Physical examination
 - Skin examination / assessment at study gel site of both legs
 - e-diary, study training

- Urine drug screen and alcohol test
 - Pregnancy test (urine) (females only)
 - Record AEs
 - Record concomitant medications
 - Subjects return home after completing procedures and assessments
- Day 1 to Day 2
 - Admission Visit: On Day 1, subjects will be admitted to the clinic. Day 1 procedures and assessments are as follows:
 - Issue e-diary (subjects will record eVAS and Categorical Qualifying Pain Assessments in e-diary prior to randomization)
 - VAS Qualifying Pain assessment. Note: Time 0 hours is the baseline time point for the first study gel application and occurs within 30 minutes of qualifying pain assessments (post-exercise inclusion criteria).
 - Categorical Qualifying Pain assessment. Note: Time 0 hours is the baseline time point for the first study gel application and occurs within 30 minutes of qualifying pain assessments (post-exercise inclusion criteria).
 - Post-exercise inclusion criteria
 - Randomization (for subjects who meet post-exercise eligibility criteria)
 - Vital signs
 - Skin examination / assessment at study gel site
 - Apply study gel according to treatment schedule

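### In a completing subject, no scheduled blood sample can start the three CK-triggered precautionary instructions of Protocol 5.2.2.1, because they end at the visit where the first post-exercise CK is drawn

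*Protocol*

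**What the plan says.** Protocol 5.2.2.1 expects CK to rise after the Day -1 exercise and adds steps to watch for rhabdomyolysis. The trigger reads "If a subject has a serum CK above 10,000 U/L", with associated elevation of LDH, AST or ALT, in a subject who has "no significant signs or symptoms of rhabdomyolysis other than muscle pain and swelling at the exercised muscles". For such a subject "the following actions will be taken with the subject until the EOS Visit", which the section gives as Day 8 for Period 1 subjects and Day 22 for Period 2 subjects. The actions are to watch urine colour, to report discoloration, and to keep hydrated (about 3.7 L of fluid a day for males, 2.7 L for females).

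Two further sets of measures carry no stated EOS limit. The optional steps (overnight stay with hydration, repeat CK, repeat urinalysis) are introduced by "In addition, the following actions may be taken with the subject at the discretion of the investigator". The work-up for suspected rhabdomyolysis closes with "Abnormalities should be followed until they have returned to baseline, or until the investigator considers them clinically stable".

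On sampling, Protocol 5.2.2 says "Blood samples will be collected according to the schedule in Table 2". The Table 2 row beginning "Clinical laboratory tests (hematology, serum chemistry, and urinalysis" is marked only at Screening and at EOS/ET. SAP 9.4 likewise names screening and EOS.

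**The concern.** The precaution is meant for subjects who feel little more than the expected soreness but whose muscle enzymes are very high. Such a subject can be recognised only by a blood test. If the first planned test falls on the day the instructions expire, routine conduct of the protocol never puts them into effect.

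The interval at stake is the days just after exercise. On Day -1, Protocol 6.3 states "Subjects return home after completing procedures and assessments". In the visible text, the only related advice given regardless of CK is in Protocol 5.3.4. It concerns hydration during the exercise regimen and has neither a fluid volume nor a urine watch.

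**Working it through.** The plan states no figure to reproduce here. The check sets the schedule against the rule.

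**Step 1: when CK is drawn.** CK, LDH, AST and ALT are all Table 3 chemistry parameters, so they follow the laboratory row of Table 2. That row is not redacted. Against its 11 columns:

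| Column | Laboratory tests |
|---|---|
| Screening (Day -30 to -2) | X |
| Exercise visit (Day -1) | none |
| Day 1, Day 2, Days 3-8 | none |
| Day 8 safety visit, Days 9-14 | none |
| Day 15 safety visit, Days 16-22 | none |
| EOS/ET (Day 8 or 22) | X |
| Follow-up call (Day 15 or 29) | none |

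The visit lists in Protocol 6.3 agree. A few items in the Day 8 safety-visit list for Period 2 are redacted, but the Table 2 row shows no laboratory test there. The Screening sample precedes the exercise and cannot show its effect. Scheduled post-exercise CK values before EOS/ET: 0.

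**Step 2: how long after exercise.** Day 1 falls 24 to 30 hours after the Day -1 exercise (Protocol 3.1), so there is no Day 0 and Day d is about d days after exercise.

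- 1-week subjects: EOS on Day 8 (+1) gives 8 to 9 days.
- 3-week subjects: EOS on Day 22 (+1) gives 22 to 23 days.

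**Step 3: set against the end of the instructions.** They end at EOS. The first scheduled sample is drawn at EOS, and the central laboratory's result comes after the draw. In a completer, the time from the first scheduled trigger sample to the end of the instructions is therefore 0 days.

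**Step 4: what else could start them.** There are two possibilities.

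- An early-termination visit (Protocol 4.3) can fall before the nominal Day 8 or 22.
- An unscheduled CK can be taken. Section 5.2.2.1 mentions further CK testing only as a discretionary repeat, or as part of the work-up once CK is raised and rhabdomyolysis is suspected. In the visible text, nothing prompts a first CK in a subject whose only signs are local pain and swelling.

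**Step 5: after EOS.** If a completer's EOS CK is above 10,000 U/L without suspicion of rhabdomyolysis, the three instructions have already lapsed. The follow-up call comes on Day 15 or 29, nominally 15 - 8 = 7 or 29 - 22 = 7 days later.

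**The case against.** The best reply is that Section 5.2.2.1 is a contingency rule. It says what to do if a high CK is found and does not promise that a scheduled sample will find it. An investigator may order a CK at any time, and Protocol 5.2.6 foresees unscheduled visits for adverse events. On this view nothing is contradictory, and universal instruction is a design preference. This stands in part: the rule can operate, and the text is not self-contradictory. It does not explain why a mandatory precaution for nearly symptom-free subjects depends on a test that neither the schedule nor the visible text calls for in time.

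A second reply is that other surveillance covers the risk. Subjects are in the clinic on Days 1 and 2, adverse events are recorded throughout, calls are made on Day 5 and later, and suspected rhabdomyolysis leads to a full work-up with open-ended follow-up. This stands and limits the consequence. It is not a full substitute, because Protocol 9.2 has subjects questioned only in general terms, without naming symptoms.

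A reader might infer that subjects receive no urine or hydration instruction at all after exercise. The documents do not support that. The content of the Day -1 training is not reproduced, the consent pages were removed and the application instructions are redacted. The statement can be made only of the visible protocol text.

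**Conclusion.** The point holds for completing subjects and scheduled samples. As written, the three mandatory instructions cannot be started by routine sampling, and they lapse at the first visit that could reveal the need for them. It rests on the unredacted laboratory row of Table 2, on Protocol 6.3 and SAP 9.4 agreeing with it, and on the day count above.

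A reader might go further and infer that the protocol has no rhabdomyolysis monitoring, or that subjects were harmed. Neither follows. The discretionary steps and the work-up are not limited by EOS. The documents also do not say how often CK passes 10,000 U/L after this exercise or when it peaks, so harm cannot be quantified.

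The efficacy analyses are unaffected. SAP 2.2.6 reports that the futility rule was met. If that stop stands and no further subjects are exercised, the change matters only for later use of this protocol. This is a minor point and a cheap improvement.

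**What to change.** Amend Section 5.2.2.1 in two places.

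- **Before EOS.** At the existing Day -1 study training, give every exercised subject the urine-colour watch, the instruction to report discoloration and advice on adequate hydration. These run through EOS regardless of CK. The stated daily fluid volumes can stay with the CK trigger. EOS is defined only for Period 1 and Period 2 participants, so name an end day (Day 8 would be one choice) and a contact route for exercised subjects who are not randomized.
- **After EOS.** Replace the fixed end at the EOS Visit. If the EOS/ET CK exceeds 10,000 U/L, the instructions run from that result until CK has fallen or the investigator considers the subject stable, with a check at the existing follow-up call. Showing that CK has fallen would need a repeat sample, which the section already allows at the investigator's discretion.

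Keep the discretionary steps and the work-up as they are. No new scheduled draw and no change to Table 2's laboratory row, SAP 9.4 or any analysis method is needed. An early scheduled CK would be an alternative, but it adds a blood draw and the documents give no CK time course from which to choose the day.

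The cost is a routine amendment under Protocol 12.4 (written agreement, IND submission and IRB/IEC approval), with updates to the Day -1 visit list, the training and the subject materials. Subjects receive more instruction, and a few more urine-colour adverse events may be reported. The instruction precedes randomization, so this would apply to both arms.
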